**FIGURE 9 – ILLUSTRATION OF STUDY POPULATION AND ACCOUNTABILITY**

## 11.5 Subject Accountability

The following terms and definitions will be used for the accountability of the study population and are based on the definitions found in ANSI Z80.29 Rev 018, section B.5.3 as modified and explained below.

- Enrolled – the total number of subjects that have signed the full informed consent.
  - Enrolled but ineligible – the total number of subjects that have signed the full informed consent but do NOT meet all of the inclusion/exclusion criteria.
  - Enrolled and eligible – the total number of subjects that have signed the full informed consent and meet all of the inclusion/exclusion criteria.
- Surgical Withdrawal – Subjects (eyes) that have been enrolled and determined eligible but do not undergo surgical preparation of the ocular surface for any reason.
- Discontinued– Subjects (eyes) that have discontinued treatment prior to the visit window associated with the form as a result of death, the removal of all 4 implant segments (explant), or any other reason except lost to follow-up.
  - Explanted Eye – Eyes that underwent implantation surgery, but have had all implanted segments removed.
- Lost to Follow-up – Subjects that have withdrawn from the study after initial eye surgery or subjects that have missed the visit window associated with the form and all subsequent scheduled visits despite documented efforts by the Investigator to schedule the subject for follow-up.
- Missed Visit – Data for subjects (primary eyes) that is not available for a follow-up visit within the specified visit window associated with the form, but data is available for a subsequent follow-up visit for such subject.

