#### Randomized Sub-study

The sample size for Objective #2 in Section 11.2 is based on the following criteria:

- The two-sided significance level = 0.05 (or one-sided significance level = 0.025).

- Based on the randomized control group data collected in IDE G970152, the 6-month responder rate is estimated as 10% for the control group.
- Based on the surgery group data collected in IDE G970152, the 6-month responder rate was lower than the 12-month responder rate. Therefore, it is assumed that the 6-month responder rate of the randomized surgery group in this study will be approximately 0.75.
- The statistical power = 90%.
- Fisher's exact test is used for sample size calculation.

Based on the criteria above, a sample of 14 randomized surgery group primary eyes and 14 randomized control group primary eyes at 6 months will ensure a power greater than 90% for Objective #2, using a one-sided alpha of 0.025.

A sample size of 30 randomized surgery group subjects and 30 randomized control group subjects has been selected which will account for a possible 10% subject drop-out rate and allow for greater accuracy in point estimates for both groups. This randomized sub-study will be conducted at 3 clinical sites. Sites will be chosen based on availability of equipment for additional sub-study measures, such as availability of an iTrace unit (Tracey Technologies, Houston, TX), and the ability and willingness of the site to participate in the additional sub-study. The target enrollment at each of the 3 sites in the randomized sub-study will be 20 eligible subjects to provide an even distribution. However, no site may enroll and determine eligible more than half of the randomized sub-study cohort or 30 subjects.

[figure not shown]

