## 11.6 Analysis of Effectiveness Cohorts

For the primary analysis of Objective #1, all observed 12-month data of the surgical primary eyes will be included in the effectiveness analysis. Missing data will not be imputed except that explanted primary eyes will be imputed as failures.

For the primary analysis of Objective #2, all reported 6-month data of the randomized primary eyes will be included in the analysis. Missing data will be imputed as follows:

- Randomized Control Group: In the absence of 6 month visit data, the nearest available data recorded between and including the 3 month visit up to the 6 month visit will be utilized. Since this randomized control group does not receive the benefit of the surgery during this 6 month observation period, the lost to follow-up and missed visit rate could be higher and since no intervention occurs during the 6 month period, this imputation of missing data is warranted. In the absence of any observed data between the 3 month visit

and 6 month visit, this missing data will not be imputed since failure to achieve the effectiveness endpoint is expected.

- Randomized Surgery Group:
  - Explanted primary eyes will be imputed as failures.
  - In the absence of 6 month visit data, the nearest recorded data after 6 months up to and including 12-month visit data will be used. This imputation is warranted as the visit data between 6 and 12 months provides a predictive indicator of 6 month results. In the absence of any observed data between 6 and including 12 months, this other missing data will not be imputed.

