### **Sensitivity Analysis of Objective #1:**

Sensitivity analysis will be performed for Objective #1 using the following imputation methods for missing 12-month data:

- **Best Case Analysis:** All discontinued primary eyes will be imputed as effectiveness failures. For primary eyes lost to follow-up or for primary eyes missing 12-month visit data, the best value from any protocol scheduled visit at 1 month or later (1 month, 3 month or 6 month visit) will be used. If such visit data does not exist for a primary eye, the effectiveness will be imputed as a success.
- **Worst Case Analysis:** All discontinued primary eyes will be imputed as effectiveness failures. For primary eyes lost to follow-up or missing 12 month visit data, the worst value from any protocol scheduled visit at 1 month or later (1 month, 3 month or 6 month visit) will be used. If such visit data does not exist for a primary eye, the effectiveness will be imputed as a failure.
- **Tipping Point Analysis:** All discontinued primary eyes will be imputed as effectiveness failures. For primary eyes missing 12-month visit data for reasons other than discontinued, effectiveness will be initially be set to success. At this step, the lower limit of the one-sided 97.5% confidence intervals (CI) will be calculated. Serial calculations will then be performed using a decreasing number (i.e.,  $n-1$ ,  $n-2$ , ...1) of successes to determine the maximum number of additional failures allowed for the lower bound one-sided 97.5% CI of the effectiveness endpoint percent estimate to achieve or exceed 75% success.

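### Objective #1's Best and Worst Case analyses ignore DCNVA measured after a missed 12-month visit, so the Worst Case can score a measured later failure as a success

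*Combined protocol and SAP*

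**What the plan says.** Section 11.5 separates two kinds of eye without a visit. A Missed Visit has no data in the window "but data is available for a subsequent follow-up visit for such subject". Lost to Follow-up covers subjects who withdrew after the first surgery and "subjects that have missed the visit window associated with the form and all subsequent scheduled visits". For a Missed Visit at 12 months, a later measurement exists by definition.

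For the primary analysis of Objective #1, section 11.6 says "all observed 12-month data of the surgical primary eyes will be included in the effectiveness analysis", and adds: "Missing data will not be imputed except that explanted primary eyes will be imputed as failures".

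In section 11.8 the Best and Worst Case analyses score discontinued eyes as failures. They then treat lost-to-follow-up eyes and eyes missing the 12-month visit alike. The Worst Case rule is that "the worst value from any protocol scheduled visit at 1 month or later (1 month, 3 month or 6 month visit) will be used"; the Best Case rule is the same with the best value. An eye with no such value becomes an assumed failure (Worst) or success (Best). The tipping-point analysis starts every non-discontinued missing eye as a success and turns them into failures one at a time.

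Table 1 and section 8.5.1 schedule visits with DCNVA at 2, 18 and 24 months as well. No Objective #1 rule names any of these three.

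**The concern.** A worst-case analysis should be at least as pessimistic as the data in hand. Here it is not: a failure measured at 18 months is set aside in favour of a success at 1, 3 and 6 months. The Best Case has the mirror fault, because a success measured at 18 months cannot rescue an eye that failed early.

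The accountability section separates eyes with later data from eyes without, and the sensitivity analyses then ignore the difference. Objective #1 is a single-arm test against 75% and one of two objectives that must both be met. A reader of the Worst Case would take it as the floor that the available data allow, and it may not be.

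**Working it through.** **1. The plan's own figure.** Inputs from sections 11.3 and 11.8: goal 75%, assumed rate 82.5%, one-sided 0.025, exact binomial lower limit, 330 evaluable eyes. The smallest count whose exact lower 97.5% limit reaches 75% is 264 of 330. Type I error is 0.0192 and power is 0.896, which agrees with the stated 90% to within half a point. The same rule gives pass marks of 259/324 and 287/360.

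**2. Windows** (section 8.5.1, 30-day months).
- 12 months: 360 ± 45 = days 315 to 405.
- 18 months: 540 ± 45 = days 495 to 585.
- 24 months: 720 ± 60 = days 660 to 780.

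**3. The rules applied to three non-discontinued eyes.**

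| Eye | 1, 3, 6 months | 12 months | 18 months | Primary | Best Case | Worst Case |
|---|---|---|---|---|---|---|
| A | responder at each | missed | failure | left out | success | success |
| B | failure at each | missed | responder | left out | failure | failure |
| C | responder at each | missed | none (lost) | left out | success | success |

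Eye A is scored exactly as eye C, although A's later failure is on file. Eye B cannot be a success even in the Best Case.

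**4. Size in the Worst Case.** That analysis gives every eye an outcome. With 360 eyes (the planned cohort) the pass mark is 287, or 287/360 = 79.7%. Each eye of type A that is rescored as a failure lowers the rate by 1/360 = 0.28 points. The plan's 10% dropout gives 360 × 0.10 = 36 eyes without a 12-month value. How many of these are type A is not stated. As assumed counts:
- 5 eyes: 5/360 = 1.4 points.
- 10 eyes: 10/360 = 2.8 points.
- 18 eyes: 18/360 = 5.0 points.

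A Worst Case with 287 + j successes still passes only if no more than j eyes are rescored.

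**5. What the tipping point covers.** Take a bare primary pass, 259/324, with all 36 missing eyes non-discontinued. The analysis starts at 259 + 36 = 295 successes of 360 and tolerates 295 − 287 = 8 failures. That range holds whatever the later exams show. It does not say how many of the 36 eyes are already measured failures.

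**The case against.** **The tipping point already bounds the problem.** This stands. A reader might infer that the planned sensitivity analyses cannot reveal poor response among people who skip the visit because they look only backward. That is true of the Best and Worst Case analyses but not of the tipping point, which uses no earlier visit and covers every possible outcome for these eyes. What is lost is the measurement itself and the meaning of the Worst Case label.

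**The wording may already allow later visits.** The phrase about any scheduled visit from 1 month onward could include 18 months. The bracketed list also omits the scheduled 2-month visit, so it may be loose drafting. Read plainly, though, the list is closed. If later visits were intended, the same edit is needed so that two programmers get the same result. Nor does the plan say whether an exam shortly after day 405 counts as observed 12-month data.

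**Later data may not exist at the analysis.** The PMA is filed when the cohort completes 12 months (sections 3.0 and 7.2). Suppose the cut falls when the last-operated eye reaches day 405. An eye operated at least 585 − 405 = 180 days earlier has its whole 18-month window behind it; one operated less than 495 − 405 = 90 days earlier has not reached that window. This limits the fix without removing the point, and the documents do not offer it as a reason.

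**Objective #2 differs.** Its surgery-group rule does use later data: "the nearest recorded data after 6 months up to and including 12-month visit data will be used". But its control-group rule looks backward, and 12-month data will normally exist when a 6-month gap is filled. The contrast supports the point without proving an error.

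**Loss of effect is not established for this implant.** A reader might infer from section 6.2 that response fades after 6 months. Section 6.2 concerns the earlier design and links the loss to displaced segments. For the redesigned implant, section 6.3 reports DCNVA of 20/40 or better in 80% (237/298), 84% (210/249) and 91% (120/132) at 12, 18 and 24 months, on shrinking denominators. Section 11.3 adds that in the earlier IDE "the 6-month responder rate was lower than the 12-month responder rate". On these figures early values could just as well understate 12-month response.

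**Conclusion.** The point holds for the Best and Worst Case analyses of Objective #1. They discard measured later DCNVA, and the Worst Case is not the worst the available data allow. It rests on reading the bracketed visit list as closed. The size is unknown: 0.28 points of the Worst Case rate per affected eye among 360, times a count the documents do not give.

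The documents do not support a stronger claim that the decisive test is biased or loses power. Adding 9 or 18 Missed Visit eyes responding at 60% to 324 observed eyes at 82.5% would cut the chance of passing from 89.9% to 84.8% or 78.5%. But the 60% and both counts are assumptions, and the sum describes a change to the primary test that is not proposed here. If those eyes responded at 82.5%, the chance would rise slightly, to 90.7% or 91.3%. An observed-case primary analysis with a tipping point is a defensible choice. The defect is limited and worth correcting because it is cheap.

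**What to change.** In section 11.8, replace the bracketed list in the Best and Worst Case rules with every scheduled DCNVA visit at 1 month or later that is available at the data cut-off. Name the 2-, 18- and 24-month visits, and include any exam made after the 12-month window closes. A later failure then counts as a failure in the Worst Case, and a later success as a success in the Best Case. Keep the rule that discontinued eyes are failures, and keep the assumed outcome only for eyes with no such exam.

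Leave the primary and tipping-point analyses unchanged. Report the number of Missed Visit eyes at 12 months and their observed later responder status.

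The cost is SAP wording and a small programming change, with no new data. There are two limits. At a cut when the cohort completes 12 months, late enrollees may have no later exam, so the count of eyes with one should be shown. And the two bounds will usually move apart, because each draws on more visits; for a worst and a best case that is the intended behaviour.

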## 11.6 Analysis of Effectiveness Cohorts

For the primary analysis of Objective #1, all observed 12-month data of the surgical primary eyes will be included in the effectiveness analysis. Missing data will not be imputed except that explanted primary eyes will be imputed as failures.

For the primary analysis of Objective #2, all reported 6-month data of the randomized primary eyes will be included in the analysis. Missing data will be imputed as follows:

- Randomized Control Group: In the absence of 6 month visit data, the nearest available data recorded between and including the 3 month visit up to the 6 month visit will be utilized. Since this randomized control group does not receive the benefit of the surgery during this 6 month observation period, the lost to follow-up and missed visit rate could be higher and since no intervention occurs during the 6 month period, this imputation of missing data is warranted. In the absence of any observed data between the 3 month visit

and 6 month visit, this missing data will not be imputed since failure to achieve the effectiveness endpoint is expected.

- Randomized Surgery Group:
  - Explanted primary eyes will be imputed as failures.
  - In the absence of 6 month visit data, the nearest recorded data after 6 months up to and including 12-month visit data will be used. This imputation is warranted as the visit data between 6 and 12 months provides a predictive indicator of 6 month results. In the absence of any observed data between 6 and including 12 months, this other missing data will not be imputed.

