## **8.8 Subject Termination or Withdrawal**

Subjects may be terminated from the study if the Investigator believes that continued participation in the study may jeopardize the subject's health or welfare. Subjects may also elect to withdraw from the study at their discretion. Every effort will be made to encourage the subject to maintain compliance with the protocol and to continue in the study. Further, every effort will be made in both instances to conduct examinations as determined by the Investigator to ensure the safety of the subject. The Sponsor should be notified promptly by the Investigator upon the termination or withdrawal of a subject by completion of the Study Exit form. Terminated or withdrawn subjects may not be replaced with additional enrolled and eligible subjects. Subjects who have all implant segments removed (explanted) from both eyes will be exited from the study after at least 3 months post-explant follow-up.

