#### Full Study Cohort Effectiveness Endpoint

The sample size calculation for the statistical hypotheses described for Objective #1 in Section 11.2 is based on the following criteria:

- The two-sided significance level = 0.05 (or one-sided significance level = 0.025).
- The statistical power = 90% at  $p = 0.825$ . The assumption of true responder rate of 0.825 is based on the simple average of success rate observed in previous Refocus clinical study data, as follows:
  - Disposable Scleratome group had an observed success rate of 88%.
  - Re-usable Scleratome group had an observed success rate of 77%.
  - Simple average of 88% and 77% is 82.5%.
- Binomial distribution is used for sample size calculation.

Based on the criteria above for Objective #1, 330 treated primary eyes should be available for analysis at 12 months. If a dropout rate of 10% of subjects by 12 months is considered, then the surgery cohort should include approximately 360 treated primary eyes.

For safety analysis, in order to detect an Adverse Event (AE) with a true probability of occurrence among subjects of 1% with 95% probability, based on the binomial distribution, a sample of at least 299 eyes would be required (in accordance with ANSI Z80 29 18Nov2013 AIOL [rev20]). Assuming a drop-out rate of approximately 10% of subjects by 12 months, the surgery cohort should include a minimum of 333 treated primary eyes.

A sample size of 333 treated primary eyes will meet the sample size requirements for both safety and effectiveness. The study cohort is planned for 360 surgery subjects at up to 14 study sites. However, no site may enroll and determine to be eligible more than 20% of the subject surgery cohort.

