#### **Analysis of Objective #1:**

The one-sided 97.5% lower confidence limit of the 12-month responder rate will be calculated based on the exact binomial distribution. This goal is met if the one-sided 97.5% lower confidence limit of the 12-month responder rate is at least 75%.

The percentage of primary eyes achieving the Effectiveness Endpoint at 12 months will be compared among the study sites. The Fisher's exact test will be used to evaluate the possible study site effect. If the site effect is significant, i.e.,  $p\text{-value} \leq 0.15$ , then 12-month responder rates stratified by study site will be provided and the average of the site 12-month responder rates will be calculated. The normal distribution approximation will be used to estimate the one-sided lower 97.5% confidence limit for the average 12-month responder rate.

Fisher's exact test will also be used to assess the effects of subject sex, race and age category at surgery on the 12-month responder rates for primary eyes using a p-value of 0.15. For this analysis, age will be categorized into 3 interval groups (i.e., 45-49, 50-54, and 55-60).

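### Objective #1: the primary analysis drops discontinued eyes that were not explanted, while all three of its sensitivity analyses count them as failures, so Best Case does not bound the primary result

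*Combined protocol and SAP*

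**What the plan says.** Section 11.6 bases the Objective #1 primary analysis on observed 12-month data from surgical primary eyes, with one exception: "Missing data will not be imputed except that explanted primary eyes will be imputed as failures".

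Section 11.5 defines a wider group. Discontinued eyes are those stopped through death, "the removal of all 4 implant segments (explant), or any other reason except lost to follow-up". An explanted eye is one sub-category. Subjects who withdraw after the first eye's surgery are placed under lost to follow-up instead.

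Section 11.8 opens each of the three Objective #1 sensitivity analyses (Best Case, Worst Case, Tipping Point) with the same rule: "All discontinued primary eyes will be imputed as effectiveness failures". Best Case then gives lost or missed eyes their best earlier value, or a success if they have none.

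Section 8.8 shows how a discontinuation without explant can arise: "Subjects may be terminated from the study if the Investigator believes that continued participation in the study may jeopardize" the subject's health or welfare.

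The decision rule in 11.8 is: "This goal is met if the one-sided 97.5% lower confidence limit of the 12-month responder rate is at least 75" per cent.

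**The concern.** The same eye is scored in two ways. If it is discontinued with the implant in place and has no 12-month result, it is absent from the primary analysis and a failure in all three sensitivity analyses. No section says why.

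Two things follow. First, a sensitivity range should contain the primary result. Here Best Case is stricter than the primary for this group, so the trial could meet its goal in the primary analysis and miss it under the most favourable sensitivity analysis. The plan does not say how to read that outcome.

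Second, an eye whose subject was stopped on health grounds is unlikely to be missing at random. Leaving such eyes out tends to raise the responder rate in a single-arm comparison with a fixed goal, and trial success depends on that comparison.

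**Working it through.** **Inputs.** From 11.3: "The two-sided significance level = 0.05 (or one-sided significance level = 0.025"); 90% power at a true rate of 0.825; exact binomial; 330 evaluable eyes; about 360 treated. From 11.8: the exact one-sided 97.5% lower limit must be at least 75%. The number of affected eyes, D, is not in the documents and is varied below.

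**Formula.** The exact lower limit for x responders among n eyes is L(x, n) = the 0.025 quantile of Beta(x, n − x + 1).

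**The plan's own figure.** L(263, 330) = 0.7495 fails and L(264, 330) = 0.7527 passes, so the pass mark is 264/330 (80.0%). P(X ≥ 264) with n = 330 is 0.0192 at p = 0.75 and 0.896 at p = 0.825. The planned 330 eyes reproduce, with power of 89.6% against the stated 90%.

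**When do the primary and Best Case disagree?** The primary uses x/n. Best Case adds D failures, plus whatever is imputed for other missing eyes.

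| Primary result | Other missing eyes | D | Best Case | Lower limit | Result |
|---|---|---|---|---|---|
| 264/330 | none | 1 | 264/331 | 0.7502 | pass |
| 264/330 | none | 2 | 264/332 | 0.7477 | fail |
| 264/330 | 23, all successes | 7 | 287/360 | 0.7519 | pass |
| 264/330 | 22, all successes | 8 | 286/360 | 0.7490 | fail |
| 272/330 (lower limit 0.7788) | none | 12 | 272/342 | 0.7486 | fail |

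Rows 3 and 4 use 360 − 330 = 30 missing eyes and the most favourable Best Case, in which every other missing eye is a success. Less favourable imputed values lower the number needed. The last row is close to the planned rate (272/330 = 82.4%), and 12 is the smallest D that reverses it.

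**Effect on false success.** Suppose the true rate over all 330 + m treated eyes is exactly 75%, m eyes are dropped, and a fraction r of those would have responded. The rate among the 330 observed eyes is p = [0.75(330 + m) − r·m]/330, and the pass probability is P(X ≥ 264 | 330, p).

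| m | p, none respond (r = 0) | Pass chance | p, half respond (r = 0.5) | Pass chance |
|---|---|---|---|---|
| 0 | 0.7500 | 1.9% | 0.7500 | 1.9% |
| 3 | 0.7568 | 3.7% | 0.7523 | 2.4% |
| 7 | 0.7659 | 7.9% | 0.7553 | 3.2% |
| 10 | 0.7727 | 13.1% | 0.7576 | 3.9% |

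The r = 0 columns are upper bounds. If the dropped eyes respond at the overall rate (r = 0.75), p stays at 0.75 and there is no inflation.

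**The case against.** The strongest reply is that the affected group is narrow. Explants are already failures, and 11.5 puts withdrawals by the subject under lost to follow-up. That leaves deaths, terminations by the investigator with the implant retained, and other unlisted reasons. This stands, and it limits the size. A reader might infer that all of the planned 10% dropout is scored inconsistently; the 11.5 definitions do not support that. They do leave the line between a withdrawal and some other reason unclear, so classification decides how an eye is scored.

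Second, the two-eye reversal is a corner case: the result must sit exactly on the pass mark with no other eye missing. This also stands, hence the 8-eye and 12-eye cases.

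Third, a reader might take 13.1% as the test's true error rate. Nothing in the documents supports ten such eyes, which would be a third of the 30 expected missing, or a zero response rate among them. The retained implant may still work.

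Fourth, primary and sensitivity rules may legitimately differ, and Worst Case and Tipping Point would show the effect. That is fair: the 11.8 rule does not prove that 11.6 is wrong. It does not explain why an analysis labelled Best Case is stricter than the primary for some eyes.

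Lastly, a reader might extend the point to every sensitivity analysis in the plan. It applies to Objective #1 only; the Objective #2 tipping point varies discontinued eyes between success and failure.

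**Conclusion.** The inconsistency is real and unexplained. For Objective #1, a discontinued eye that was not explanted and lacks 12-month data is ignored by the decisive test and failed by all three sensitivity analyses. Best Case is therefore not an upper bound on the primary, and a primary pass beside a Best Case failure is possible.

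Whether it would matter depends on a count that the plan does not give. A result on the pass mark is vulnerable to between 2 and 8 such eyes, depending on how many others are missing and how they are imputed. A result near the planned rate needs about a dozen even with no other eye missing. The inflation of false success is small to moderate: it stays below 4% for up to ten dropped eyes if half respond, and reaches 13.1% only if all ten are non-responders. The documents do not show that the primary analysis will be materially biased; they show that it can be, in the sponsor's favour, through a rule that the plan does not apply elsewhere for this objective. It should be settled before database lock.

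**What to change.** - **11.6:** for Objective #1, score as failures all discontinued primary eyes, as defined in 11.5, that lack 12-month data. Keep the existing rule for explants.
- **Deaths:** 11.5 counts death as a discontinuation. If deaths unrelated to the device are to be exempt, exempt them in 11.6 and in all three Objective #1 analyses in 11.8; an exemption in 11.6 alone would recreate the mismatch.
- **11.5:** state that terminations by the investigator count as discontinued and withdrawals by the subject as lost to follow-up, and fix this before database lock.

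Section 8.8 needs no change for this purpose. In particular, an acuity measurement at an exit before month 12 could not enter an analysis confined to 12-month data.

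The cost is a few sentences and a slightly lower stated responder rate: five such eyes would take 264/330 = 80.0% to 264/335 = 78.8%. At the pass mark that also changes the result, since the lower limit for 264/335 is 0.7403.

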### **Sensitivity Analysis of Objective #2:**

- **Tipping Point Analysis:** All discontinued primary eyes will be iteratively imputed as effectiveness success or failures. Let  $n_1$  and  $n_2$  be the number of discontinued primary eyes for the randomized surgery group and the randomized control group, respectively. For the  $n_1$  discontinued randomized surgery group primary eyes, they can be imputed as 0 failures, 1 failure, 2 failures, and up to  $n_1$  failures, for a total of  $(n_1+1)$  possible imputations. For the  $n_2$  discontinued randomized control group primary eyes, there are  $(n_2+1)$  possible imputations. Therefore, there are  $(n_1+1) \times (n_2+1)$  possible combinations of success and failure imputations for these discontinued

primary eyes. For each of these possible imputations, the lower limit of the one-sided 97.5% confidence intervals (CI) will be calculated. The imputations that have the lower one-sided 97.5% CI < 75% will be identified.

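### The only sensitivity analysis for Objective #2 (section 11.8) does not test Objective #2: it applies Objective #1's 75% limit and varies only discontinued eyes

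*Combined protocol and SAP*

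**What the plan says.** Section 11.2 defines Objective #2 as superiority: the surgery group's 6-month responder rate exceeds the control group's. Section 11.8 tests this with a two-sided Fisher's exact test. Neither place sets a 75% threshold. The 75% lower limit is the criterion for Objective #1, the single-arm 12-month rate (section 11.8, analysis and sensitivity analysis of Objective #1).

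For a missing 6-month value in the randomized surgery group, section 11.6 says "the nearest recorded data after 6 months up to and including 12-month visit data will be used". For Objective #1 the same section says "explanted primary eyes will be imputed as failures", and its list for the randomized surgery group repeats that rule for Objective #2. Control gaps are filled from data between the 3- and 6-month visits.

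Section 11.5 separates three categories. A missed visit has no data in the window, "but data is available for a subsequent follow-up visit for such subject". Discontinued covers death, "the removal of all 4 implant segments (explant), or any other reason except lost to follow-up". Lost to follow-up stands apart and includes withdrawal after the first surgery.

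The only sensitivity analysis listed for Objective #2 begins "All discontinued primary eyes will be iteratively imputed as effectiveness success or failures" and ends "The imputations that have the lower one-sided 97.5% CI < 75% will be identified". It does not say whether the limit is for the surgery rate or for the difference between groups.

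On the planning side, section 11.3 says that in the earlier study "the 6-month responder rate was lower than the 12-month responder rate". It assumes 0.75 at 6 months and 0.825 at 12 months ("Simple average of 88% and 77% is 82.5"%).

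**The concern.** A tipping-point analysis should show how far missing outcomes would have to go against the result before its conclusion is lost. This one has three faults.

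- **Wrong criterion.** It asks whether a lower limit falls below 75%, which is not the question of Objective #2.
- **Wrong eyes.** The eyes whose 6-month values are borrowed from later are missed visits under section 11.5, not discontinued eyes, so their values stay fixed. Lost-to-follow-up eyes are not varied either. By the plan's own statement the borrowed values are expected to favour surgery slightly, so these are the eyes that most need checking.
- **Conflict with the primary rule.** Explants are discontinued by definition, so the analysis may count them as successes.

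This is the trial's only randomized comparison, and both objectives must be met. A robustness table that flags almost everything, for a reason unrelated to the hypothesis, would mislead a reader of the results.

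**Working it through.** **Inputs.** Rates 0.75 (surgery, 6 months), 0.10 (control) and 0.825 (12 months), 30 eyes per arm, two-sided 0.05: section 11.3. The numbers of filled, discontinued and explanted eyes are not in the plan and are assumed below.

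**1. The plan's own figure.** Exact power is the sum of binomial probabilities over all tables where two-sided Fisher p ≤ 0.05 in favour of surgery. At 14 per arm it is 93.4%, which agrees with the stated figure of over 90%. At 30 per arm it is 99.98%.

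**2. The 75% limit read as the surgery rate.** The exact lower limit L for x of 30 solves P(X ≥ x | 30, L) = 0.025.

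| Responders | Lower limit |
|---|---|
| 22/30 | 54.1% |
| 23/30 | 57.7% |
| 27/30 | 73.5% |
| 28/30 | 77.9% |

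So 28 responders are needed. P(X ≥ 28) is 1.1% at a true rate of 0.75 and 8.4% at 0.825. A result of 22/30 against 3/30 has Fisher p = 9.5 × 10⁻⁷ but a surgery limit of 54.1%, and would be flagged with no eye imputed at all.

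**3. The grid as written.** Assume three discontinued, non-explanted eyes per arm, with 20/27 and 3/27 observed. Surgery is then (20 + i)/30 and control (3 + j)/30 for i, j = 0 to 3, giving 4 × 4 = 16 combinations.

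| Criterion | Range | Result |
|---|---|---|
| Lower limit of surgery rate | 47.2% to 57.7% | 16 of 16 below 75% |
| Newcombe lower limit of difference | 21.8 to 43.1 points | 16 of 16 below 75 |
| Two-sided Fisher p | 2.4 × 10⁻⁷ to 0.0006 | 16 of 16 significant |

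Reading the limit as that of the difference does not help. The planned difference is 75 − 10 = 65 points, already under 75, and even 30/30 against 3/30 gives a lower limit of only 70.7.

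**4. Eyes that are varied.** With three forward-filled eyes and no discontinued eyes, n1 = n2 = 0. The grid has (0+1) × (0+1) = 1 combination, and nothing is varied. Varying those three eyes against Objective #2's own test gives 20 to 23 of 30 against 3/30, with p at most 1.1 × 10⁻⁵. Starting from 22/30 against 3/30, significance survives 11 reversals from success to failure (p = 0.030) and is lost at 12 (p = 0.057).

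**5. Size of the fill.** Shift = k × gap / 30, where k is the number of filled eyes (assumed).
- Gap 82.5 − 75 = 7.5 points: 3 × 7.5/30 = 0.75 point; 6 × 7.5/30 = 1.5 points.
- Gap 88 − 75 = 13 points (using the disposable-Scleratome rate): 3 × 13/30 = 1.3 points; 6 × 13/30 = 2.6 points.

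The standard error of the surgery rate is √(0.75 × 0.25/30) = 7.9 points.

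**6. Effect on the Fisher test.** With 3 or 6 eyes filled at 0.825, power is 99.98% to 99.99%. For type I error, take both true 6-month rates as 0.10. With six filled eyes at 0.10 + 0.13 = 0.23, the chance of a rejection favouring surgery is 0.0130, below 0.025. Counting both directions it is 0.0151, below 0.05.

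**7. Explants.** Assume two explants and 21 responders among the other 28 eyes. Section 11.6 gives 21/30 = 70.0%. The section 11.8 grid also admits 23/30 = 76.7%.

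**The case against.** The tipping point carries no decision rule. Flagged combinations are only identified, and success rests on sections 11.2 and 11.8's Fisher test. That stands: the 75% figure, perhaps carried over from the Objective #1 text, cannot change the trial's verdict. It also stands that three discontinued, non-explanted eyes in the surgery arm would be unusual, because section 11.5 counts withdrawal after surgery as lost to follow-up. But the flag does not depend on the grid: any surgery count below 28 of 30 triggers it under the surgery-rate reading. Few discontinued eyes also means that little is varied. On explants, the grid does contain the combination with every explant a failure, so the conflict adds misleading rows rather than overriding the primary analysis.

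A reader might infer that the forward fill endangers the primary test. The documents do not support that. The fill is pre-specified with a stated reason, and at the planning rates its shift is small against the standard error.

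Nor is an upward shift certain: section 11.3 gives a direction from an earlier study but no size. A reader might look to section 6.2 for evidence of a reversal. The loss of effect there concerned displaced segments of an earlier design, which the same section says the redesign corrected. Section 8.5.3 might seem to supply extra values between months 6 and 12, but it does not say that the primary eye's DCNVA is measured at the separate fellow-eye visits.

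**Conclusion.** The concern holds for the sensitivity analysis in section 11.8 and is minor. As written, the analysis uses a criterion that is not Objective #2's, leaves out forward-filled and lost-to-follow-up eyes, and conflicts with the explant rule in section 11.6. At the planned rates nearly every combination would be flagged while the between-group result is overwhelming. The primary rule in section 11.6 does not need to change, and the Fisher verdict is very unlikely to. These sizes rest on the planning rates in section 11.3 and on assumed counts of 3 or 6 filled eyes, 3 discontinued eyes per arm and 2 explants. The finding of a mismatched criterion and mismatched eye categories rests on the text alone.

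**What to change.** Keep the section 11.6 rule for the primary analysis. Replace the Objective #2 tipping-point text in section 11.8 with wording such as:

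> The analysis set is the Objective #2 part of the effectiveness cohort in section 11.4: randomized surgery-group primary eyes implanted with at least one segment, and randomized control-group primary eyes. Every eye in this set without observed 6-month visit data (discontinued other than by explant, lost to follow-up, or missed visit) is set in turn to success or failure. Explanted eyes remain failures. With n1 and n2 such eyes in the two groups, each of the (n1+1) × (n2+1) combinations is reported with its two-sided Fisher's exact p-value and the difference in 6-month responder rates with a 95% Newcombe interval. Combinations with p > 0.05, or with a surgery rate not above the control rate, are identified.

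Add one analysis of observed 6-month data only, with explants as failures. For illustration, 20/27 against 3/30 gives p = 7.3 × 10⁻⁷ and a difference of 64.1 points (39.7 to 78.4).

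The cost is SAP wording and a little more analysis, with no new data. The observed-only analysis is slightly less precise: with 27 surgery eyes the standard error is √(0.75 × 0.25/27) = 8.3 points, against 7.9 with 30.
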